## **6.2. Description of data gathering methods, including definitions of variables.**

The majority of data needed for this project will be sourced from the *Western Australian Patient Blood Management System*. The advantages of sourcing the majority of data from one system include consistent data collection processes and classification of variables.

The exposure variables of interest are degree of anaemia and red blood cell transfusion. Anaemia will be defined using the nadir haemoglobin result during admission for those not transfused and the pre-transfusion haemoglobin result in patients transfused, as described previously. The pre-transfusion haemoglobin will be the closest level measured prior to the first red blood cell transfusion administered. Fridges are available for storing blood in theatres and because of this the timing of red blood cell transfusion in the operating room is unknown. Therefore for patients transfused in the operating room the nadir haemoglobin result will be used as a surrogate for the pre-transfusion haemoglobin result. Haemoglobin levels will be grouped into the following categories: below 50 g/L, 50-59 g/L, 60-69 g/L, 70-79 g/L, 80-89 g/L, 90-99 g/L, 100 g/L or over. These cutoffs were selected after reviewing similar studies.

The main outcome variables of interest are mortality and hospital length of stay of current admission. For the mortality analysis, both in-hospital and 30-day all-cause mortality will be assessed. In-hospital and 30-day mortality will be calculated from date of death recorded in hospital patient admission systems (TOPAS/WebPas). Potential confounders collected will include age at admission, sex, hospital, discharge year, admission type (emergency or elective), clinical specialty, and patient comorbidities.

Patient comorbidities will be assigned a score based on the Charlson Comorbidity Index derived from ICD-10 codes for the comorbidities identified. To ensure the Charlson score represents patient comorbidities on admission, hospital-acquired complications will be excluded from the calculation.

Other data items to be collected include admission date, discharge date, discharge specialty, diagnosis related group, hours in ICU, presence of a red blood cell transfusion (yes/no), had a massive transfusion (yes/no), and number of red blood cell units transfused.

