Some observational studies in the surgical setting have sought to address this gap in the literature by comparing outcomes between patients transfused and those not transfused across various levels of anaemia. For example, in patients undergoing cardiac surgery, Shaw and colleagues used a propensity-matched analysis to compare the outcomes of patients transfused to those not transfused at four preoperative haematocrit levels (a measure of anaemia). They found that transfused patients had higher mortality rates than those not transfused, at all levels of haematocrit. Kougais and colleagues studied the impact of postoperative nadir haemoglobin levels and transfusion on outcomes in patients presenting for elective operations for atherosclerotic vascular occlusive disease at one hospital. They found that neither red blood cell transfusion nor nadir haemoglobin level was associated with the composite end point of death and/or myocardial infarction. Interestingly, there was no significant interaction between transfusion and nadir haemoglobin, suggesting transfusion had the same effect on outcome regardless of the nadir haemoglobin level.

While these studies provide some insights into differences between outcomes in transfused and non-transfused anaemic patients they also leave many unanswered questions. For example, what are the outcomes in patients with haemoglobin thresholds lower than 70 g/L?

Two case series have investigated mortality in patients with very low haemoglobin levels who do not receive red blood cell transfusions. These studies found that each 10 g/L decrease in haemoglobin below 80 g/L was associated with a 1.8 to 2.5 times increased odds of mortality, with sharper increases in mortality observed when the haemoglobin fell below 50 g/L. However, these studies do not address what effect red blood cell transfusion would have on outcomes at various nadir haemoglobin levels.

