### **6.3. Validity and reliability of data**

The research methodology for this project is based on methodologies used in similar studies. To improve the validity of results, potential confounding variables will be statistically adjusted for in the analysis, and inpatients receiving transfusions other than red blood cells will be excluded.

This study will investigate consecutive adult surgical admissions to three public hospitals for specialties where blood is commonly transfused. Given the study design and the broad inclusion criteria applied, the results are expected to have external validity and are likely generalizable to other surgical inpatients admitted to large teaching hospitals internationally.

Exposure and outcome variables have been carefully selected and are known to be accurately measured. Results from laboratory testing will be used to measure nadir haemoglobin values to accurately define the degree of anaemia. The cut-offs for haemoglobin levels have been selected based on other studies.

The in-hospital and 30-day mortality outcome measures selected for this study are well-defined objective measures and will be coded as binary variables (yes/no). Hospital length of stay, also a frequently studied objective outcome measure will be calculated in days from admission to discharge. All outcomes variables will be measured in the same way between the different subgroups.

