### **6.4. Statistical methods.**

Exposure and outcome variables will initially be described by univariate and bivariate statistics, the latter using the chi-squared test for categorical variables and independent samples t-test for continuous variables. Logistic regression models will be applied to test the relationship that both red blood cell transfusion and nadir haemoglobin levels have with in-hospital mortality and 30-day mortality. A zero-truncated negative binomial regression model will be applied to the length of stay outcome. All regression models will adjust for the same potential confounders. A robust variance adjustment will be applied to the regression models to account for any potential correlation between multiple admissions for the same patient.

For this analysis we are also interested in whether the presence of a red blood cell transfusion modifies the effect of nadir haemoglobin on in-hospital mortality, 30-day mortality and length of stay. To test any effect modification on outcome an interaction term between nadir haemoglobin level and red blood cell transfusion will be added to the multivariable logistic regression models. Only significant interactions (defined as p-values <0.05) will be reported, with calculated odds ratios for interaction terms presented.

In addition, Kaplan-Meier curves and Cox proportional hazards models will be plotted to show time to death in patients transfused red blood cells when compared to patients not transfused red blood cells across the various nadir haemoglobin levels.

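### Untransfused, ward-transfused and theatre-transfused patients are banded on different haemoglobin values, which biases the within-band comparison towards apparent harm from transfusion

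*Protocol*

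**What the plan says.** Section 6.2 sets the haemoglobin variable by transfusion status: "Anaemia will be defined using the nadir haemoglobin result during admission for those not transfused and the pre-transfusion haemoglobin result in patients transfused". For transfused patients it adds: "The pre-transfusion haemoglobin will be the closest level measured prior to the first red blood cell transfusion administered". Timing is unknown for units given in theatre, so there is an exception: "for patients transfused in the operating room the nadir haemoglobin result will be used as a surrogate for the pre-transfusion haemoglobin result".

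The values are cut into seven bands: "below 50 g/L, 50-59 g/L, 60-69 g/L, 70-79 g/L, 80-89 g/L, 90-99 g/L, 100 g/L or over". Section 6.3 then treats the result as a single variable: "Results from laboratory testing will be used to measure nadir haemoglobin values to accurately define the degree of anaemia". Section 6.4 also calls it nadir haemoglobin for everyone and uses it in the logistic models and across the Kaplan-Meier and Cox analyses. For effect modification, "an interaction term between nadir haemoglobin level and red blood cell transfusion will be added to the multivariable logistic regression models", and "Only significant interactions (defined as p-values <0.05) will be reported".

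The protocol describes no analysis with a common definition or with haemoglobin aligned in time.

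**The concern.** Three kinds of measurement share one axis:

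- **Untransfused:** lowest value of the whole stay. Membership of the 70-79 g/L band means the patient never measured below 70, which is known only at discharge or death.
- **Transfused on the ward:** last value before the first unit. Nothing is implied about later values.
- **Transfused in theatre:** lowest value of the whole stay, which may have been measured after the transfusion it stands in for.

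Both objectives in Section 3 compare transfused with untransfused patients at a given haemoglobin. If one group is guaranteed not to have fallen further and the other is not, the groups differ in prognosis for a reason created by the definition. Section 4 says the results may guide the thresholds chosen for future randomised trials, so a built-in tilt towards harm matters.

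**Working it through.** **Direction.** A whole-stay minimum cannot exceed any earlier value from the same stay. For ward-transfused patients the assigned value is therefore at or above their true nadir, while for untransfused patients it equals the nadir. Misbanding goes one way only. Section 5 reports, from untransfused patients, that "each 10 g/L decrease in haemoglobin below 80 g/L was associated with a 1.8 to 2.5 times increased odds of mortality". Transfused patients in a band thus include some with the higher risk of a lower band. The confounders listed in Section 6.2 (age, sex, hospital, year, admission type, specialty, comorbidity) do not measure later falls, so adjustment does not remove this.

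**Hand approximation.** The protocol has no figure of its own to reproduce. Let s be the share of a band's transfused patients who later fall one band, g the odds ratio per band (1.8 or 2.5, Section 5), and t the share transfused in theatre. With rare deaths and no transfusion effect:

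spurious OR ≈ 1 + (1 − t) × s × (g − 1)

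Neither s nor t is in the protocol, so both are assumed.

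| s | t | g = 1.8 | g = 2.5 |
|---|---|---|---|
| 10% | 0 | 1 + 0.10 × 0.8 = 1.08 | 1 + 0.10 × 1.5 = 1.15 |
| 50% | 0 | 1 + 0.50 × 0.8 = 1.40 | 1 + 0.50 × 1.5 = 1.75 |
| 50% | 50% | 1 + 0.25 × 0.8 = 1.20 | 1 + 0.25 × 1.5 = 1.375 |

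**Simulations in which death follows the realised nadir.** Daily haemoglobin paths were simulated with no direct effect of transfusion on death. Transfusion triggers, later falls and baseline risk are assumptions. So are the gradients of 1.0-1.3 per 10 g/L between 80 and 100 and 2.5 below 50. The common odds ratios for transfusion, adjusted for band, were:

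| Scenario | Plan's rule, no theatre patients | Plan's rule, with theatre patients | Whole-stay nadir in both groups |
|---|---|---|---|
| Haemoglobin triggers transfusion (9% of transfused truly in a lower band) | 1.16 to 1.25 | 1.12 to 1.18 (60% theatre) | 1.09 to 1.12 |
| Bleeding also triggers it (14% in a lower band) | 1.18 to 1.44 | 1.11 to 1.28 (50% theatre) | 1.06 to 1.12 |

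The last column is residual confounding within 10 g/L bands, so not all of the excess comes from the unequal definition. Dividing it out in the second scenario gives 1.18/1.057 = 1.12 up to 1.44/1.12 = 1.29 without theatre patients, and 1.114/1.057 = 1.05 up to 1.281/1.12 = 1.14 with half in theatre.

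With 65,000 admissions (the midpoint of Section 6.5), the transfusion term was falsely significant at 0.05 in 14-49% of 100 replicates in the first scenario, against 8-11% with a common nadir. In the second it was 4 to 54 of 60 replicates across settings, against 3 to 7 of 60.

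**Simulations in which death follows the untreated nadir.** Here transfusion has no effect at all. With assumed daily changes of SD 2-4 g/L and a flat gradient above 80, the 70-79 g/L odds ratio was 1.64-2.57 without theatre patients and 1.15-1.64 with half in theatre. A further run, in which transfusion did not raise haemoglobin, gave about 1.3-2.4 under the rule and about 1.0-1.5 with a common nadir. Bands below 70 are not quoted, because untransfused deaths there were too few.

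**Interaction.** If s and g are the same in every band, the formula gives the same spurious OR in every band and no interaction. In the realised-nadir scenarios, false interactions occurred in 4-9% of replicates against 6-8% with a common nadir, and in 1 to 9 of 60 against 2 to 5 of 60. In the untreated-nadir scenario with a flat gradient above 80, they occurred in 7-45% against 2-5%, falling to 2-15% against 2-7% with half in theatre. When the 2.5 gradient was continued above 80, the odds ratios at 90-99, 80-89 and 70-79 were 1.82, 1.79, 1.77 (SD 2) and 2.65, 2.34, 2.75 (SD 4). The bias remained, but the trend across bands did not.

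**The case against.** The rule has a rationale. It follows an earlier study that the protocol cites, it avoids banding ward-transfused patients on values already raised by transfusion, and the theatre surrogate is disclosed with its reason. The theatre exception also removes the asymmetry for those patients. Section 6.1 excludes massive transfusion and recipients of plasma, platelets or cryoprecipitate, which plausibly removes many continuing bleeders. An SAP that is not shown may add sensitivity analyses.

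These points limit the size of the bias and do not cancel it. The exclusions leave ordinary later falls in place. The theatre rule shrinks the asymmetry only in proportion to an unknown share, and it lets post-transfusion values into the exposure. The unequal rule itself is fixed in the protocol.

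A reader might infer that the rule by itself manufactures an interaction, with apparent harm growing as haemoglobin falls. The documents do not support that. Section 5 gives a gradient below 80 g/L, with sharper rises below 50, and is silent above 80. The rising pattern needs a flat gradient above 80 and largely disappears when the gradient continues. Distortion of the interaction test is possible but does not follow from the rule alone.

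A reader might also infer that the nadir analysis must be dropped. Section 3 asks about levels of nadir haemoglobin, so replacing it outright would change the stated question.

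**Conclusion.** The point holds for the main comparison. Section 6.2 places non-comparable haemoglobin values on one axis, and the error runs in one direction, towards apparent harm from transfusion. That direction needs only two things: mortality that rises as haemoglobin falls, and some ward-transfused patients who fall lower after the first unit.

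The size cannot be derived from the protocol, which gives neither the share falling lower nor the share transfused in theatre. Under the assumed scenarios the spurious mortality odds ratio runs from about 1.1 to above 2, and it is smaller when more patients are transfused in theatre. Part of it is within-band confounding that a common definition would not remove. The values above 2 come from scenarios in which death follows the untreated nadir. Length of stay was not quantified.

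For objective 2 the supportable statement is that the interaction test may be distorted, by an amount that depends on how the gradient and later falls differ between bands.

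**What to change.** Prespecify a time-aligned analysis for objectives 1 and 2. Among patients not yet transfused, compare those transfused with those not transfused at the same most recent haemoglobin, using sequential cohorts or a model with time-varying haemoglobin and transfusion. Report it alongside the nadir-band analysis. State in advance that the nadir-band odds ratios and interaction will not be interpreted as a transfusion effect if the two disagree, and what will count as disagreement.

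Add two supporting analyses:

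- Repeat the analyses without theatre-transfused admissions, because their transfusion timing is unknown.
- Use the whole-stay nadir in both groups as a common-definition sensitivity analysis, noting that it includes post-transfusion values in transfused patients.

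In Sections 6.3 and 6.4, stop calling the mixed variable nadir haemoglobin without qualification.

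The cost is protocol wording and extra programming. The timed haemoglobin results and ward-transfusion times are already implied by the pre-transfusion rule. Theatre-entry time is not among the listed data items, so a pre-theatre haemoglobin value would need additional data. The time-aligned estimate also has a different meaning, transfused now versus not now, and should be labelled so.

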## **6. Research Plan**

### **6.1. Description of population and sample.**

This project will include all adults admitted as elective or emergency cases for selected surgical specialties to three hospitals in Western Australia between July 2008 and June 2017. Local studies show that the following six specialties account for the majority of blood transfused in surgical patients.

- Orthopaedics
- Gastrointestinal Surgery
- Vascular Surgery
- Urology
- Cardiothoracic surgery
- Neurosurgery

Any patients transfused fresh frozen plasma, platelets, and cryoprecipitate will be excluded from the study. This is to reduce the possibility of confounding as the purpose of this study is to focus on nadir haemoglobin levels, red blood cell transfusion and their effect of mortality and length of stay.

Also excluded are patients receiving a massive transfusion (defined as 5 units of red blood cells in 4 hours or 10 units in 24 hours), patients transfused any blood products 90 days prior to admission, patients with a length of stay of less than 2 days (same day and overnight admissions), patients under the age of 18 years at admission, and patients with no haemoglobin results.

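### The first haemoglobin of the admission is not in the adjustment set, so patients admitted at a low level and patients who fell to it are compared as alike within each haemoglobin band

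*Protocol*

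**What the plan says.** Protocol Section 6.2 defines the haemoglobin exposure as a single value per admission. For untransfused patients: "Anaemia will be defined using the nadir haemoglobin result during admission for those not transfused". For transfused patients it is the "closest level measured prior to the first red blood cell transfusion administered". Where the transfusion was given in theatre its timing is unknown, and the nadir stands in. The value is then grouped into seven bands.

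The adjustment set is in the same section: "Potential confounders collected will include age at admission, sex, hospital, discharge year, admission type (emergency or elective), clinical specialty, and patient comorbidities". A second list begins "Other data items to be collected include admission date, discharge date, discharge specialty, diagnosis related group, hours in ICU" and goes on to transfusion indicators and unit counts. Neither list contains a first or admission haemoglobin. Section 6.4 adds: "All regression models will adjust for the same potential confounders".

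Section 6.1 enrols "all adults admitted as elective or emergency cases for selected surgical specialties" and excludes "patients with no haemoglobin results", so every included admission has at least one result. Section 6.3 presents the exposure as well measured: "Results from laboratory testing will be used to measure nadir haemoglobin values to accurately define the degree of anaemia".

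**The concern.** Objective 1 is a contrast between transfused and untransfused patients at a given haemoglobin level. A patient admitted at 75 g/L and one who falls from 140 to 75 g/L enter the same band. They may differ in bleeding, in the chance of transfusion and in the chance of death. The band records where the haemoglobin ended, not where it started, and no listed covariate records the start.

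The protocol's own Synopsis gives reason to expect that the starting level matters. It reports that 39% of surgical patients were anaemic on admission, with three-fold higher odds of death and a five-fold greater likelihood of transfusion. A variable that is associated with both exposure and outcome and is present at admission is a candidate confounder.

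Two results are at stake: the transfusion association within each band and, for objective 2, the interaction. If the mix of admitted-low and fell-to-low patients changes from band to band, the bias changes too and can look like effect modification.

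**Working it through.** The protocol states no effect size or power for this contrast, so there is no figure to reproduce. The check has three parts.

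**1. What the text fixes.** The list in Section 6.2 names age, sex, hospital, discharge year, admission type, specialty and comorbidity. Section 6.4 applies the same confounders in every model. No section adds the first haemoglobin.

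**2. Association ignoring the band.** From the Synopsis: prevalence of admission anaemia 0.39, mortality ratio 3, transfusion ratio 5 (read here as an odds ratio). Assumed: 5%, 10% or 20% of admissions transfused. Let p1 and p0 be the prevalence of admission anaemia in transfused and untransfused admissions. Solve

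- share × p1 + (1 − share) × p0 = 0.39, with p1/(1 − p1) = 5 × p0/(1 − p0)
- bias factor = (1 + (3 − 1) × p1) / (1 + (3 − 1) × p0)

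| Transfused (assumed) | p1 | p0 | Bias factor |
|---|---|---|---|
| 5% | 0.747 | 0.371 | 2.494/1.742 = 1.43 |
| 10% | 0.731 | 0.352 | 2.462/1.704 = 1.44 |
| 20% | 0.696 | 0.314 | 2.391/1.627 = 1.47 |

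This shows that the cited associations are not trivial. It is not the bias of the planned analysis, which already conditions on the haemoglobin band.

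**3. Association within a band.** The protocol has no within-band figures, so every input is assumed: no true transfusion effect; the fall from first to band-defining haemoglobin normally distributed with SD 15 or 20 g/L; 3% mortality and 40% transfused at the mean fall; odds ratios of 1.1, 1.2 or 1.3 per 10 g/L for both death and transfusion. With D(f) and T(f) the logistic risks at fall f, averaged over f:

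- risk if transfused = E[D·T]/E[T]
- risk if untransfused = E[D·(1 − T)]/E[1 − T]
- apparent odds ratio = odds of the first divided by odds of the second

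| Odds ratio per 10 g/L | SD 15, same direction | SD 20, same direction | SD 15, opposite | SD 20, opposite |
|---|---|---|---|---|
| 1.1 | 1.02 | 1.04 | 0.98 | 0.96 |
| 1.2 | 1.08 | 1.14 | 0.93 | 0.88 |
| 1.3 | 1.16 | 1.29 | 0.86 | 0.77 |

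In the opposite-direction columns a larger fall raises the odds of one of death and transfusion and lowers the odds of the other. With SD 10 g/L the same-direction values shrink to 1.01, 1.03 and 1.07. Changing the transfused share from 5% to 80% at SD 20 leaves the first two same-direction values at about 1.04 and 1.14 and moves the third only between 1.29 and 1.31.

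For the interaction, if two bands differ only in the spread of the fall (SD 20 against 15, odds ratio 1.3), the apparent ratio of odds ratios is 1.292/1.160 = 1.11 with no true modification.

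A coarser version uses admission anaemia as a yes/no factor, with 30% transfused, 39–80% admitted anaemic, a transfusion odds ratio of 0.5–2 and a mortality ratio of 0.5–3. It gives bias factors of about 0.83 to 1.20.

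**The case against.** The strongest reply has five parts.

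- **The confounder list may not be closed.** It says what will be included, and an analysis plan could add to it. This stands as a caution. But the protocol also lists the extract fields, and Section 6.7 has the extraction code deleted six months after extraction, so a field left out now may be hard to recover.
- **Part of the problem is already handled.** Excluding massive transfusion and anyone given plasma, platelets or cryoprecipitate removes many of the heaviest acute bleeders. Admission type, specialty and Charlson score capture more. This stands: the calculation is not adjusted for these, so it does not measure the residual bias. None of them records the starting haemoglobin, however.
- **First haemoglobin is an imperfect marker.** An emergency patient who bled before arrival also presents low. A reader might infer that the covariate cleanly separates acute loss from chronic anaemia; it does not.
- **It may not precede transfusion.** Section 6.2 says theatre transfusion times are unknown, so a first result taken after theatre could itself reflect transfusion. This stands and shapes the fix.
- **Availability is inferred.** Finding a nadir and a closest pre-transfusion value requires dated results, so the first should be obtainable. The protocol does not say that the full series is extracted, and those values could be fields derived in the source system.

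A reader might also infer that the investigators considered this variable and set it aside as unavailable. Nothing in the protocol says so; it is simply not mentioned.

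**Conclusion.** The point holds as a gap in the adjustment set. The protocol lists its confounders and extract fields without the first haemoglobin, although its Synopsis describes admission anaemia as associated with both exposure and outcome. The within-band contrast and its interaction may therefore be confounded.

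The protocol supports the possibility of confounding but not its size or sign. The illustrative range for the apparent odds ratio, about 0.77 to 1.29 when the truth is 1, rests wholly on assumed spreads and associations and ignores the listed proxies. It is tempting to conclude that the omission makes transfusion look harmful. That needs the fall to act in the same direction on death and transfusion within a band, which the protocol does not show. The factors of 1.43 to 1.47 ignore the band and should not be read as the expected bias. The change is worth making before extraction because it is cheap and specific.

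**What to change.** Before extraction:

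1. Add the value and date/time of the first haemoglobin of the admission to the Section 6.2 data items, after confirming with the data custodian that it can be drawn from the results used for the nadir and pre-transfusion values.
2. Describe it by transfusion status within each haemoglobin band.
3. Add it as a continuous spline covariate to the logistic, length-of-stay and Cox models, and report results with and without it.
4. For patients transfused in theatre, use a first result dated before the day of surgery where the source allows this. Flag the others and repeat the analysis without them. Date of surgery is not a listed item, so it would have to be requested too.

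The cost is one extra field (two with date of surgery), one covariate and a second set of model results. The protocol should also state the limits: the covariate adds nothing where the first result is also the band-defining result; it separates acute from chronic anaemia imperfectly when bleeding began before admission; and the haemoglobin main effect changes meaning, because with the first value in the model it describes the level reached given the starting level.
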